4.2.2 Safety in Hemodialysis Patients

A review of the aggregate safety data shows that CR845 was well tolerated in hemodialysis patients when administered after each dialysis session for up to 8 weeks at IV doses ranging from 0.5 mcg/kg to 6 mcg/kg. Although patients exposed to CR845 reported more adverse events compared with placebo patients, most events were mild or moderate in nature. Generally mild, transient paresthesias (facial tingling) and/or hypoesthesias (in different anatomic locations), mostly on the first week of dosing, as well as headache, dizziness, and somnolence, were the most frequently reported adverse events associated with CR845 administration. Of note, side effects (eg, dysphoria and hallucinations) commonly associated with centrally-acting kappa opioids were not reported in patients exposed to CR845. Consistent with its lack of affinity for mu-opioid receptors, CR845 did not cause euphoria, respiratory depression, or reduction in oxygen saturation.

CR845-CLIN2101 (Part A) evaluated the safety, pharmacokinetics, and efficacy of repeated IV doses of CR845 compared to placebo over an 8-week treatment period in 174 hemodialysis patients. This study is the longest treatment period evaluated to date in hemodialysis patients and no clinically important or significant safety findings related to CR845 were noted. As expected with patients on hemodialysis, a significant number of the reported serious adverse events (SAEs) were considered not treatment-related, but related to the disease and/or comorbid conditions. There were 31 (17.8%) of 174 patients randomized and treated in the study who had treatment-emergent SAEs. Of the 31 SAE reports, 4 (9%) occurred in 45 placebo-treated patients and 27 (21%) in 129 CR845-treated patients. Only 1 SAE of mental status changes (moderate in severity) in a patient who received CR845 1.5 mcg/kg IV was considered by the Investigator to be probably related to study drug. However, based on the Sponsor's medical review, an alternate etiology of urgent/emergent hypertension offers a more plausible explanation for the acute change in mental status. There were 4 patient deaths (2.3%) in the study, all of which were considered not related to the study drug.

In patients with normal renal function, CR845 can cause free-water diuresis (aquaresis) and increased serum sodium. However, as would be expected in patients undergoing dialysis in whom there are few functioning nephrons, there was no evidence of aquaresis or significant increases in serum sodium concentrations. There were no adverse trends in clinical chemistry or hematology values (drawn pre-dialysis), including, no apparent differences between the placebo and CR845 groups in serum sodium. There were no discernable differences between treatment groups in vital sign results. Of particular note, among patients receiving CR845, there was no apparent reduction in blood pressure or respiratory rate following dosing.

Adverse event summary tables can be found in the [Investigator's Brochure](#), with further details of the safety profile of CR845.

4.2.3 Efficacy of CR845 in Hemodialysis Patients with Uremic Pruritus

The efficacy of CR845 in uremic pruritus was evaluated in two Phase 2, randomized, double-blind, placebo-controlled studies (CR845-CLIN2005 [Part B] and CR845-CLIN2101 [Part A]).

CR845-CLIN2005 (Part B) included 65 hemodialysis patients with moderate-to-severe uremic pruritus who received either IV CR845 1.0 mcg/kg (n=33) or placebo (n=32) 3 times per week for 2 weeks, after each hemodialysis session. CR845 significantly decreased itching intensity compared with placebo (p=0.016), as measured by a visual analog scale (VAS) and significantly improved quality of life related to itching (Skindex-10 Scale) (see [Investigator's Brochure](#) for details). Furthermore, CR845-treated patients exhibited statistically significant reductions in both daytime (p=0.03) and nighttime (p=0.007) worst itching scores compared with placebo, and the reduction in itching intensity scores was similar on dialysis and nondialysis days. The

mean change from baseline VAS curves over time showed numerical separation between the treatment groups within the first week of treatment.

CR845-CLIN2101 (Part A) evaluated the safety, pharmacokinetics, and efficacy of repeated IV doses of CR845 compared to placebo over an 8-week treatment period in 174 hemodialysis patients experiencing moderate-to-severe uremic pruritus daily or near-daily for 4.4 years on average. The study was conducted at 33 dialysis centers and assessed the effect of 3 doses of CR845 (ie, 0.5 mcg/kg, n=44; 1 mcg/kg, n=41 and 1.5 mcg/kg, n=44) or placebo (n=45) administered at the end of each dialysis session (ie, 3 times/week). The primary efficacy endpoint for Study CR845-CLIN2101 (Part A) was based on itch intensity measurement and defined as the change from a 1-week baseline recorded prior to the start of study drug to the last week of the 8-week treatment period with respect to the weekly mean of the daily 24-hour Worst Itching Intensity numerical rating scale (NRS) score. The least squares (LS) mean (\pm standard error [SE]) treatment group difference from placebo at Week 8 across all CR845 doses was -1.3 (\pm 0.41) (95% confidence interval [CI]: -2.1 to -0.5) ($p=0.002$) with an average NRS score reduction from baseline of -3.2 (\pm 0.22) (LS mean \pm SE) and 95% CI ranging from -3.7 to -2.8. Examination of the individual CR845 dose group results for the Full Analysis Population indicates that a substantial improvement over placebo was observed with all 3 doses. These differences from placebo were statistically significant for the lower dose group of 0.5 mcg/kg ($p<0.001$) and the 1.5 mcg/kg group ($p=0.019$), with an effect size estimated as 0.82, 0.39, and 0.62 for the 0.5, 1.0, and 1.5 mcg/kg doses, respectively. Average reduction from baseline (LS mean \pm SE) ranged from -2.8 (\pm 0.38) in the 1.0 mcg/kg dose group (95% CI ranging from -3.5 to -2.0) to -3.8 (\pm 0.38) in the 0.5 mcg/kg dose group (95% CI ranging from -4.5 to -3.1).

4.2.4 Pharmacokinetics in Hemodialysis Patients

CR845 is eliminated primarily through the kidney and no major metabolites have been identified in humans. Consequently, total body clearance of CR845 in patients with severe renal impairment is reduced relative to healthy, matched, control patients (CR845-CLIN1005) such that plasma levels of CR845 remain relatively constant until cleared during dialysis in hemodialysis patients (CR845-CLIN1003 and CR845-CLIN2005 [Part A]). Half-life ranges between 26 and 34 hours in hemodialysis patients compared to a typical range of 2 to 3 hours in patients with normal renal function. Thus, lower doses of CR845 can be administered at a less frequent interval in hemodialysis patients to achieve the same or higher overall exposure compared to individuals with normal renal function. Based on this pharmacokinetic profile, CR845 does not need to be administered more than 3 times a week after each hemodialysis session, which is convenient for this patient population and ensures treatment compliance in a population already burdened with complex medication schedules.

The pharmacokinetic profile of repeat-dose CR845 was studied in 24 hemodialysis patients who received doses of 0.5, 1.0, or 2.5 mcg/kg 3 times per week for 1 week (CR845-CLIN2005 [Part A]). In this study, there were dose-proportional increases in

maximum concentration and area under the curve, and minimal to no accumulation with repeat doses due to clearance of the drug by hemodialysis (see [Investigator's Brochure](#) for details).

4.3 Summary of Potential Risks and Benefits

During preclinical development, no specific safety findings to preclude the use of CR845 in humans were observed. During early clinical development, IV CR845 was administered to healthy volunteers; patients with mild, moderate, or severe renal impairment, including end-stage renal disease (ESRD) and hemodialysis patients; recreational poly-drug users; and postsurgical patients. The effects of CR845 have been shown to be in line with the underlying pharmacological mechanism of KOR activity. Consistent with the nonclinical abuse liability studies conducted to date, the results of an abuse-potential study in humans indicated that CR845 appears to present a low risk for abuse potential in humans in comparison to currently clinically used opioids.

Overall, tingling/numbness, dizziness, fatigue and/or drowsiness/somnolence have been the most common adverse events. Precaution is recommended in the operation of machinery for patients who experience dizziness, fatigue, and/or drowsiness/somnolence. This is described in the informed consent form (ICF), as appropriate, and will be discussed with each patient prior to initiation of the study. In general, CR845 appeared to be well tolerated in both single- and repeat-dose clinical studies, which support continued study and development of this compound.

5.0 Objectives

Primary Objective

- To evaluate the efficacy of IV CR845 at a dose of 0.5 mcg/kg compared to placebo in reducing the intensity of itch in hemodialysis patients with moderate-to-severe pruritus.

Secondary Objectives

- To evaluate the efficacy of IV CR845 at a dose of 0.5 mcg/kg compared to placebo in improving itch-related quality-of-life measures in hemodialysis patients with moderate-to-severe pruritus.
- To evaluate the safety of IV CR845 at a dose of 0.5 mcg/kg in hemodialysis patients with moderate-to-severe pruritus.

6.0 Investigational Plan

6.1 Overall Study Design and Plan: Description

This is a multicenter, randomized, double-blind, placebo-controlled study to evaluate the safety and efficacy of IV CR845 at a dose of 0.5 mcg/kg administered after each dialysis session. The study includes a Double-blind Phase and an Open-label Extension Phase. CR845 will be evaluated relative to placebo over a 12-week Double-blind Treatment Period in hemodialysis patients with moderate-to-severe pruritus followed by a 2-week monitored Discontinuation Period. At the end of the Discontinuation Period, patients who received at least 30 doses of study drug during the 12-week Double-blind Treatment Period will have the option to receive open-label CR845 for an additional 52 weeks.

6.1.1 Double-blind Phase

The Double-blind Phase of the study will consist of a Screening Visit, a 7-day Run-in Period, a 12-week Double-blind Treatment Period, and a 2-week Discontinuation Period. Informed consent will be obtained prior to performing any study-specific procedures. The Screening Visit will occur within 7 to 28 days prior to randomization in order to assess eligibility. The Screening Visit can be conducted during the Run-in Period at the discretion of the Investigator.

6.1.1.1 Screening Visit

During the Screening Visit, patients will sign the Informed Consent, and will be evaluated for eligibility by assessment of inclusion/exclusion criteria, medical history, physical examination, prescription dry body weight, pre-dialysis 12-lead electrocardiogram, pre-dialysis vital signs, pre-dialysis hematology and serum chemistry, serum pregnancy test for females of childbearing potential, adverse events, and ESA and IV iron doses, and prior medications.

6.1.1.2 Run-in Period

Eligible patients will complete a 7-day Run-in Period during the week prior to randomization to confirm eligibility, starting on the first dialysis session of that week (ie, Monday for patients on a Monday-Wednesday-Friday dialysis schedule or Tuesday for patients on a Tuesday-Thursday-Saturday dialysis schedule). The purpose of the Run-in Period will be to confirm that each patient has moderate-to-severe pruritus (ie, weekly average score >4), as measured by the 24-hour Worst Itching Intensity NRS, and to establish a baseline itch intensity. These criteria for eligibility should not be communicated to the patients. This period will also be used to record each patient's use of itch medications.

During the first visit of the Run-in Period, patients will be trained on completion of the 24-hour Worst Itching Intensity NRS scale and will start the reporting of their Worst Itching Intensity NRS daily score. For consistency, patients will be requested to

complete the NRS worksheets (either at home or in the dialysis unit, as required) at a similar time of day around the normal start time of their dialysis.

Patients will also be trained on other itch-related patient-reported outcome (PRO) and patient health assessment worksheets during the Run-in Period or on Day 1 of the Double-blind Treatment Period.

A Structured Safety Evaluation will be performed during the Run-in Period (preferably on Wednesday/Thursday). The Structured Safety Evaluation is performed by study staff using a list of specific signs/symptoms (eg, mental status change, falls, gait disturbance).

6.1.1.3 Double-blind Treatment Period

If patients continue to meet all inclusion and no exclusion criteria at the end of the 7-day Run-in Period, they will be randomized into the Double-blind Treatment Period in a 1:1 ratio to receive either IV CR845 0.5 mcg/kg or placebo. Patients will be stratified according to their use or non-use of concomitant medications to treat their itch during the week prior to randomization (Run-in Period) as well as the presence or absence of specific medical conditions.

Day 1 of the Double-blind Treatment Period will be defined as the day of administration of the first dose of study drug and will occur on the first dialysis session day of the first treatment week (ie, Monday for patients on a Monday-Wednesday-Friday dialysis schedule or Tuesday for patients on a Tuesday-Thursday-Saturday dialysis schedule).

Patients will be administered CR845 or matched placebo as an IV bolus after the end of each dialysis session during the 12-week Double-blind Treatment Period so that each patient will receive CR845 or placebo 3 times weekly for a total of up to 36 doses.

During the Double-blind Treatment Period, patients will continue to report their Worst Itching Intensity NRS score on a daily basis, covering the previous 24 hours. In addition, during selected study visits, they will complete other PRO measures (Skindex-10 Scale, 5-D Itch Scale, and Patient Global Impression of Change). Patients will be instructed to record patient-reported outcome measurements, including Worst Itching Intensity NRS scores, at a similar time of day, whether in the dialysis unit (on dialysis days) or at home (on non-dialysis days).

Blood samples for inflammatory biomarkers will be collected for all randomized patients prior to dialysis on Day 1 and prior to the last dialysis at the End-of-Treatment Visit for the Double-blind Treatment Period (Day 85).

Clinical laboratory tests and vital signs will be monitored periodically, and adverse events and concomitant medications will be continuously recorded starting at the Screening Visit until the end of the Discontinuation Period or Early Termination Visit. Electrocardiograms (ECGs) will be monitored at Screening Visit and Day 85 or Early Termination Visit.

The number and reason(s) for missed dialysis as well as the use of antipruritic medications, iron, and erythropoiesis-stimulating agents (ESAs) will be recorded throughout the study.

A Structured Safety Evaluation will be performed weekly (preferably on Wednesday/Thursday) during the Double-blind Treatment Period. The Structured Safety Evaluation is performed by study staff using a list of specific signs/symptoms (eg, mental status change, falls, gait disturbance).

6.1.1.4 Double-blind Discontinuation Period

The Double-blind Treatment Period will be followed by a 2-week Discontinuation Period, during which no study drug will be administered and patients will be monitored for potential physical dependence, as follows:

- Daily patient completion of the Short Opiate Withdrawal Scale (ShOWS-Gossop 1990) (paper worksheet to be filled by each patient at home on nondialysis days and at the dialysis unit on dialysis days at similar time of the day for a given patient) (see worksheet in Appendix 6, Section 14.6)
- Completion of an Objective Opiate Withdrawal Scale (OOWS) worksheet (Handelsman 1987) by a trained observer at each dialysis visit (ie, 3 times a week) (see worksheet in Appendix 7, Section 14.7) (training of observer will be recorded)
- Recording of adverse events, medication used, body temperature, and vital signs at each dialysis visit.

Measurements will be taken starting at the end of the Treatment Period (Day 85) and then at each dialysis visit for up to 2 weeks following study drug discontinuation until Day 98 (Table 2).

During this Discontinuation Period, at each dialysis visit, patients will be asked to continue to report their daily Worst Itching Intensity NRS score over the previous 24 hours. In order to minimize bias, the OOWS and ShOWS will be introduced to the patients as health-assessment scales.

On the day of a dialysis visit, the OOWS and the ShOWS will be completed during the first hour (+1-hour window allowed) of dialysis so that dialysis-associated patient fatigue should minimally interfere with the completion of the scales. Double-blind study drug treatment assignment will remain blinded throughout the course of the Discontinuation Period. For patients who withdraw from the Double-blind Treatment Period early, every attempt will be made to conduct the 2-week Discontinuation Period.

A Structured Safety Evaluation will be performed weekly (preferably on Wednesday/Thursday) during the Discontinuation Period. The Structured Safety Evaluation is performed by study staff using a list of specific signs/symptoms (eg, mental status change, falls, gait disturbance).

6.1.2 Open-label Extension Phase

Patients who received at least 30 doses of study drug (either placebo or active) during the 12-week Double-blind Treatment Period and continue to meet other eligibility criteria will have the option to receive open-label CR845 for an additional 52 weeks. The Open-label Extension Phase will be comprised of the Open-label Treatment Period and the Follow-up Period. The first visit and first dosing for the Open-label Extension Phase of the study will occur during the week (+1-week window) following the Discontinuation Period. Each patient will receive CR845 at a dose of 0.5 mcg/kg after each dialysis session, 3 times per week for up to 52 weeks, whether they had been previously administered placebo or CR845. Prescription dry weight will be recorded every 12 weeks; if there is a >10% change from the previous recorded dry weight, then the CR845 dose will be adjusted.

During selected study weeks, patients will complete the 5-D Itch Scale.

[figure not shown]
Clinical laboratory tests, vital signs, adverse events, and concomitant medications will be monitored throughout the Open-label Treatment Period. Blood samples for inflammatory biomarkers will be collected periodically until the End-of-Treatment or Early Termination Visit. An electrocardiogram will be monitored at the End-of-Treatment or Early Termination Visit.

The number and reason(s) for missed dialysis will be recorded throughout the study. Use of antipruritic medications, iron, and ESAs will be recorded throughout the Open-label Treatment Period.

The last dose of open-label study drug will be administered at the last dialysis visit in Week 52. A final safety Follow-up Visit will be conducted 7-10 days after the End-of-Treatment/Early Termination Visit.

The study schematic is shown in [Figure 1](#).

Figure 1. CR845-CLIN3102 Study Schematic

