6.4.1 Treatments Administered

The study drug will be dispensed by qualified staff members who have received training on study drug handling and administration.

Patients will receive IV CR845 at a dose of 0.5 mcg/kg or placebo after each dialysis session, generally 3 times per week for up to 64 weeks (ie, 12 weeks double-blind and 52 weeks open-label) as an IV bolus into the venous line of the dialysis circuit at the end of each dialysis session and may be given either during or after rinse back of the dialysis circuit. If a patient receives additional dialysis during a given week for any reason, an additional dose of CR845 or placebo will be administered following dialysis. A maximum of 4 doses per week is allowed. No additional doses will be given for patients receiving an additional unscheduled ultrafiltration treatment.

Following the IV push of study drug, the venous line must be flushed with at least 10 mL of normal saline.

The patient's prescription dry body weight (ie, the target post-dialysis weight, as determined by the patient's nephrologist or dialysis unit during screening) will be used to calculate the dose of the study drug to be administered throughout the Double-blind Treatment Period.

During the Open-label Treatment Period, the volume of CR845 to be administered will be based on patient's prescription target dry body weight recorded on Day 1 of the Open-label Treatment Period, and adjusted if prescription dry body weight changes by $\pm 10\%$ or more from dry body weight being used for calculation of CR845 dose.

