Concomitant medications (including antipruritic medications)	Record on an ongoing basis ^l 							

ESA = erythropoiesis-stimulating agent; IV = intravenous

- a. Each visit during the Open-label Treatment Period will coincide with the patient's normal dialysis treatments. The study visit may occur on any chosen dialysis day of a scheduled week as long as all assessments are completed during that visit. Patients who miss one of the scheduled study visit weeks (eg, Week 4) may complete the visit procedures for this visit at their next dialysis treatment as long as it is within 2 weeks of the originally scheduled visit date.
- b. The End-of-Treatment Visit will be the first dialysis visit following the last dose of study drug (ie, first dialysis on Week 53).
- c. Day 1 of the Open-label Treatment Period corresponds to the week after the Discontinuation Period of the Double-blind Phase (+1 week window allowed).
- d. Prior to dosing on Day 1 of the Open-label Treatment Period, the inclusion/exclusion criteria will be confirmed.
- e. The prescription dry body weight will be captured from the dialysis prescription and will be recorded on Day 1 and every 12 weeks during the Open-label Treatment Period (during Weeks 12, 24, 36, and 48). If there is a >10% change in prescription dry body weight, then the CR845 dose will be adjusted. The date of prescription dry body weight change will also be recorded.
- f. Electrocardiogram must be performed prior to the start of dialysis.
- g. Vital signs, including body temperature, heart rate, and blood pressure, will be obtained at the specified visits while the patient is in a sitting or semi-recumbent position prior to the start of dialysis. Heart rate will be measured at each dialysis; if the heart rate is clinically significant and outside the prespecified visits per Schedule of Events the heart rate will be recorded on the relevant CRF page.
- h. Doses of ESA and IV iron administered will be recorded for the 4-week period ending on Weeks 4 (Day 1 to Week 4), 12 (Week 9 to 12), 24 (Week 21 to 24), 36 (Week 33 to 36), and 52 (Week 49 to 52) or for the 4 weeks before Early Termination Visit. Preferably record at the end of the specified week, which corresponds to the beginning of the following calendar week (ie, end of Week 4 is the Monday/Tuesday of Week 5)

- i. Administered after each dialysis as an IV bolus.

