8.0 Statistical Methods

8.1 General Considerations

This section describes the statistical analysis of efficacy and safety data collected during the Double-blind Phase only. The analysis of safety and efficacy data collected during the Open-label Phase will be included in the SAP.

The SAP will provide a detailed description for the handling of missing data, patient eligibility criteria for the analysis, and statistical methodology. If differences occur between analyses of double-blind data described in the SAP and the current protocol, those found in the SAP will assume primacy. In addition, the SAP will provide details for the analysis of data collected during the Open-label Phase, including the analysis of safety data during exposure to CR845 across both the Double-blind and the Open-label Phases.

Unless otherwise noted, continuous variables will be summarized using number of non-missing observations, mean, standard deviation, median, minimum, and maximum; categorical variables will be summarized using the frequency count and the percentage of patients in each category. In addition to the descriptive summaries, pertinent data listings will be provided.

All analyses will be performed using SAS[®] version 9.2 or higher, unless otherwise specified.

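### The open-label re-dosing rule is written against two different reference weights, and the version in the synopsis and Section 6.1.2 lets gradual weight change go uncorrected

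*Protocol*

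**What the plan says.** The intended open-label dose is fixed per kilogram. Section 6.1.2 of the protocol says "Each patient will receive CR845 at a dose of 0.5 mcg/kg after each dialysis session, 3 times per week for up to 52 weeks". Three wordings then tell the site when to recalculate it.

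- **Synopsis (Study Design) and Section 6.1.2**, in identical words: "if there is a >10% change from the previous recorded dry weight, then the CR845 dose will be adjusted". In both places this follows directly on the statement that dry weight is recorded every 12 weeks.
- **Section 6.4.1 (Treatments Administered):** the volume is based on the "prescription target dry body weight recorded on Day 1 of the Open-label Treatment Period", and is adjusted on a change, in either direction, of 10% "or more from dry body weight being used for calculation of CR845 dose".
- **Section 6.5.2, Table 3 footnote e:** "If there is a >10% change in prescription dry body weight, then the CR845 dose will be adjusted". No reference weight is named. The same footnote sets the records at Day 1 and "every 12 weeks during the Open-label Treatment Period (during Weeks 12, 24, 36, and 48").

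The only precedence sentence, in Section 8.1, begins "If differences occur between analyses of double-blind data described in the SAP and the current protocol". It ranks the SAP over the protocol for those analyses and does not reach dosing. The SAP leaves the open-label phase to a separate document (SAP Sections 1 and 2.2.2).

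**The concern.** The wordings differ in two respects. The reference is the previous record in one and the weight behind the current dose in the other. The threshold is more than 10% in one and 10% or more in the other. The second difference matters only at exactly 10%; the first matters more.

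At Week 12 the previous record and the dosing weight are the same number, the open-label Day 1 weight. From Week 24 they can differ, because a change too small to trigger re-dosing still becomes the new previous record. A rule that compares only neighbouring records therefore forgets every earlier uncorrected change. A patient who gains or loses weight steadily can move well beyond 10% from the weight used for dosing without ever triggering an adjustment.

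Two sites could thus give the same patient different doses, each citing the protocol, and a monitor could not say which had deviated. What is at stake is the delivered dose in a phase meant to describe safety at 0.5 mcg/kg for up to 52 weeks.

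**Working it through.** The plan gives no figure of its own to reproduce, so the check applies both rules to the scheduled records.

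**Inputs**
- Stated dose 0.5 mcg/kg (Section 6.1.2).
- Records at Day 1 and Weeks 12, 24, 36 and 48 (Table 3 footnote e).
- Rule A (synopsis, 6.1.2): re-dose if the weight differs from the previous record by more than 10%.
- Rule B (6.4.1): re-dose if the weight differs from the weight in use by 10% or more.
- Assumption, not in the documents: weight changes by the same percentage s, in the same direction, at each of the four records, and each weight is held until the next record. Both rules are tested only at those records.

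**Formulas**
- Delivered dose at a record = 0.5 × (weight used for dosing ÷ current weight).
- Under Rule A with every step at or below 10%, the dosing weight never changes, so the dose after k records is 0.5/(1+s)^k, with s negative for a loss.
- 52-week mean = [12 × (d0 + d12 + d24 + d36) + 4 × d48] / 52.

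**Where the rules first part.** Rule B triggers by Week 48 once the cumulative change reaches 10%:
- gain: 1.10^(1/4) − 1 = 2.41% per record;
- loss: 1 − 0.90^(1/4) = 2.60% per record.

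At 2% per record, 1.02^4 = 1.082 and 0.98^4 = 0.922, so neither rule triggers and they agree throughout.

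**Delivered dose under Rule A (mcg/kg)**

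| Step per record | Day 1 | Wk 12 | Wk 24 | Wk 36 | Wk 48 | 52-wk mean |
|---|---|---|---|---|---|---|
| +3% | 0.500 | 0.485 | 0.471 | 0.458 | 0.444 | 0.476 |
| −3% | 0.500 | 0.515 | 0.531 | 0.548 | 0.565 | 0.527 |
| +5% | 0.500 | 0.476 | 0.454 | 0.432 | 0.411 | 0.461 |
| −5% | 0.500 | 0.526 | 0.554 | 0.583 | 0.614 | 0.546 |

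**Same paths under Rule B**

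| Step per record | Resets | Wk 48 dose | 52-wk mean | Gap in means as a share of 0.5 |
|---|---|---|---|---|
| +3% | Wk 48 (1.03^4 = 1.126) | 0.500 | 0.480 | 0.9% |
| −3% | Wk 48 (0.97^4 = 0.885) | 0.500 | 0.522 | 1.0% |
| +5% | Wks 24 and 48 (1.05^2 = 1.1025) | 0.500 | 0.489 | 5.6% |
| −5% | Wk 36 (0.95^3 = 0.857) | 0.526 | 0.521 | 5.2% |

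Worked example, +5%:
- Rule A: [12 × (0.500 + 0.476 + 0.454 + 0.432) + 4 × 0.411]/52 = 0.461.
- Rule B: [12 × (0.500 + 0.476 + 0.500 + 0.476) + 4 × 0.500]/52 = 0.489.

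The gap percentages are taken from unrounded means.

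**Limits.** Four steps of exactly 10% escape Rule A entirely: 0.5/1.10^4 = 0.342 and 0.5/0.90^4 = 0.762 mcg/kg. These need a weight change of +46% or −34%; they are mathematical bounds, not expectations. Rule B keeps the dose at recorded weights between 0.5/1.10 = 0.455 and 0.5/0.90 = 0.556 mcg/kg.

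**The case against.** The strongest reply is that Section 6.4.1 is the dosing section and the only place that says how the open-label volume is calculated. The synopsis and 6.1.2 are design summaries, and footnote e can be read to agree with 6.4.1 except at exactly 10%. A site preparing a syringe would probably use 6.4.1 with the site file and pharmacy manual, which were not available for this check. That limits how often the weaker rule would be followed. It does not remove the conflict: 6.1.2 is an operative section and no clause ranks it below 6.4.1. Reading its previous record as the dosing weight is also strained, because the phrase follows the 12-weekly recording schedule.

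The size also rests on an assumed drift. Prescription dry weight is a target set by the nephrologist or dialysis unit, and may move in irregular steps. This stands. A 3% step already implies a cumulative change of about 11.5% (loss) to 12.6% (gain) for a 1% difference in mean dose. The 5% to 6% difference needs about 18.5% loss or 21.6% gain.

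Section 6.4.1 ties its trigger to no schedule, and footnote e also asks for the date of any weight change. Adjustment between records may therefore be intended, and the gaps would then differ from those shown. That qualifies the figures but does not affect the finding that the references differ.

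Finally, the consequence is small. The double-blind phase doses on the screening weight throughout, and Phase 2 gave 1.0 and 1.5 mcg/kg for 8 weeks. No safety threshold is claimed to be crossed.

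**Conclusion.** The concern holds and is minor. The protocol contains two re-dosing rules with different reference weights, and the one in the synopsis and Section 6.1.2, followed literally, does not hold the dose at its target when weight changes gradually in one direction. With equal steps tested only at the four scheduled records, the practical difference ranges from nothing at 2% per record to 5% to 6% of the stated dose over 52 weeks at 5% per record. The documents do not say what drift to expect. The effect is confined to open-label dosing and exposure; the double-blind phase, the primary endpoint, the sample size and the SAP analyses are untouched.

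**What to change.** Use the Section 6.4.1 rule everywhere. In the synopsis, Section 6.1.2 and Table 3 footnote e, state that the dose is adjusted when prescription dry body weight has changed by 10% or more, in either direction, from the weight currently used to calculate the CR845 dose. This settles both the reference weight and the threshold. The same edit could usefully say whether the check is made only at the 12-weekly records or whenever the prescription changes, and the site file and pharmacy manual should be checked for agreement.

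The cost is three wording changes, with no change to design, sample size or analysis.
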